Regimen E screening will also be utilized for final analyses. TEAEs will be summarized by the number of events of a given classification experienced by participants in each cohort and treatment group and by the number and proportion of participants experiencing such an event in each cohort and treatment group. The number of events and proportion of participants experiencing TEAEs will be summarized without regard to MedDRA term for any TEAE, any serious TEAE, any severe TEAE, any related TEAE, and any TEAE leading to discontinuation of study drug. TEAEs will be summarized by MedDRA system organ class and preferred term for the following groups of TEAEs: all TEAEs, serious TEAEs, severe TEAEs, related TEAEs, and TEAEs leading to discontinuation of study drug. TEAEs and serious TEAEs will also be summarized by MedDRA system organ class and preferred term by cohort, treatment group, and time after randomization in the following intervals: 0 to 24 weeks (168 days), 24 to 48 weeks (336 days), and 48 to 72 weeks (504 days) or longer.

Clinical efficacy analyses (Aim 2): The median survival, decline of ALSFRS-R and SVC (in that order of priority) of IV trehalose treated EAP participants (Cohorts 1, 2) will be compared to predicted placebo progression using historical placebo controls. Such a historical placebo comparison group will be created using the pooled resource open access clinical trials (PRO-ACT) and the Natural History Consortium Study in ALS databases, which are available to the PIs will be used for completing these analyses. Propensity score stratification or model-based prediction approaches will be used for placebo control group creation from these databases. Both visual inspection and a time-to-event analysis (survival) or repeated measures analysis (ALSFRS-R and VC) will be used to compare the two groups.

For each participant in the EAP and historical control analysis data set, we will estimate their propensity score and calculate a propensity score stratification factor. Additionally, for each participant treated in the EAP, we will create a set of model-based predicted placebos. Each treated participant together with their model-based predictions will define a model-based stratification factor. Both propensity score and model-based prediction analyses will utilize a set of baseline covariates that are included in both the historical control database and the EAP.

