4.9.2 Adverse Events

Participants will be monitored for adverse events from the time they sign consent for the EAP until completion of their participation as defined in the schedule of assessments.

Severity of AEs

Severity of AEs will be graded as Mild, Moderate, Severe. Missing grades will not be imputed, the AEs with missing grade will be summarized into the category of 'Not Reported' in the tabulation summary.

Relationship of AEs to Study Drug

The relationship of AE to study drug will be determined by Investigator. The relatedness categories include Related and Not Related.

TEAEs

AEs with the date of onset or worsening on or after the date of the first dose of study drug administration will be considered treatment emergent.

TEAEs Summary

AEs with onset after informed consent obtained but before the first dose of study drug will be collected but excluded from adverse event tabulations and presented in listing, only TEAEs are included in the summary by treatment cohort and overall for FAS. The number and percentage of participants with TEAEs will be presented for the summaries as described in **Table 6**. For table of overall summary, the number of events will also be provided.

Table 6 TEAE Summaries

Endpoint	Description
Overall summary	
 • TEAE • TEAE related to study drug • Serious TEAE

Endpoint	Description
	
 • Serious TEAE related study drug • Severe TEAE • Severe TEAE related study drug • TEAE leading to study drug dose reduced • TEAE leading to study drug interrupted • TEAE leading to study drug discontinuation • TEAE leading to early study discontinuation • TEAE leading to death (i.e., outcome is fatal)
TEAE	
 • Overall summary by SOC and PT • Overall summary by SOC, PT, and maximum severity grade • Overall summary by SOC, PT, and time to onset • Overall summary by PT
Most frequently-occurring ($\geq 5\%$) TEAE related to study drug	
 • Overall summary by PT
TEAE related to study drug	
 • Overall summary by SOC and PT • Overall summary by SOC, PT, and maximum severity grade • Overall summary by SOC, PT, and time to onset
Most frequently-occurring ($\geq 5\%$) TEAE related to study drug	
 • Overall summary by PT
Serious TEAE	
 • Overall summary by SOC and PT • Overall summary by SOC, PT, and time to onset

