Serious TEAE related to study drug	
 • Overall summary by SOC and PT
Severe TEAE	
 • Overall summary by SOC and PT
Severe TEAE related to study drug	
 • Overall summary by SOC and PT
TEAE leading to study drug discontinuation	
 • Overall summary by SOC and PT
TEAE leading to early study discontinuation	
 • Overall summary by SOC and PT
TEAE leading to death	
 • Overall summary by SOC and PT

- Time to onset is defined as the number of days from the date of the first dose of study drug administration to the date of AE start. The time to onset will be categorized as the following intervals: 0 to 12 weeks, 12 to 24 weeks, and > 24 weeks.
- The summary of most frequently-occurring ($\geq 5\%$) TEAE includes the TEAEs experienced by at least 5% participants in the FAS.
- For AE counting at participant level: A participant having the same event (SOC or PT) more than once will be counted only once. When summarizing events by causality and severity by participants, each participant will be counted only once within a SOC or a PT by using the event with the greatest relationship and maximum severity within each classification.

- For TEAE tables by SOC and PT, the AEs will be presented in descending order of total frequency of both SOC and PT within each SOC. If multiple SOCs or PTs have the same frequency, then they will be sorted in alphabetical order. For TEAE tables by PT only, the AEs will be listed in the descending order of total frequency.

AE listings

Individual listings for the following adverse events will be provided:

- Adverse events
- Serious adverse events
- Adverse events leading to early study discontinuation
- Adverse events leading to death

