7. CHANGES FROM AND ADDITIONS TO METHODS PLANNED IN THE PROTOCOL

The protocol Section 9.0 mentioned: for cohort 2, the TEAEs and biomarker NfL levels data collected during the parent HEALEY ALS Platform Trial Regimen E study will be combined with cohort 2 data in this EAP study for final analyses.

Changes in SAP: this is re-evaluated by sponsor and decided that the Regimen E study data will not be included in the analysis plan provided by Everest. The integration analysis of EAP study and Regimen E study data may be scheduled in-house by sponsor.

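### The protocol plans TEAE event counts by classification, but the SAP's SOC and PT tables report participants only, and SAP Section 7 does not declare the change

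*Protocol*

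**What the plan says.** Protocol 9.0, Safety Analyses (Aim 1), sets two measures for TEAEs. The first is events: "TEAEs will be summarized by the number of events of a given classification experienced by participants in each cohort and treatment group". The second is participants: "by the number and proportion of participants experiencing such an event in each cohort and treatment group". A separate sentence then deals with totals: "The number of events and proportion of participants experiencing TEAEs will be summarized without regard to MedDRA term for any TEAE", and likewise for serious, severe, related and discontinuation TEAEs. Two further sentences call for summaries by SOC and PT (the second also by time interval) without restating the measure.

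SAP 4.9.2 sets the measure for the planned tables: "The number and percentage of participants with TEAEs will be presented for the summaries as described in" Table 6. It then makes one addition: "For table of overall summary, the number of events will also be provided". A note under Table 6, headed as a rule for participant-level counting, says: "A participant having the same event (SOC or PT) more than once will be counted only once". On listings it says: "Individual listings for the following adverse events will be provided"; these cover all AEs, serious AEs, and AEs leading to study discontinuation or death.

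SAP Section 1 says that changes from the protocol's statistical methods are described in Section 7. Section 7 covers one subject, the parent-trial data. It recalls that "for cohort 2, the TEAEs and biomarker NfL levels data collected during the parent HEALEY ALS Platform Trial Regimen E study will be combined" with the EAP data, and says that this will no longer be done in this analysis.

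**The concern.** The EAP gives a weekly infusion for up to 24 weeks and has long-term safety as a stated objective. Infusion-related AEs are documented weekly, and Protocol 6.7.4 requires infusion and infusion-site reactions to be recorded as AEs. Recurrence data are therefore collected. With repeated dosing, a reader of the safety tables wants to know how many people had a given reaction and also whether it came back. A participant count answers the first question only.

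The protocol appears to have planned for both. If the SAP drops event counts by term without saying so, a summary bearing on the safety objective is lost, and nobody reading Section 7 would know. SAP Section 1 adds that the results might enter a regulatory submission.

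**Working it through.** **1. What the protocol sentence covers.** It does not name SOC or PT, so its scope has to be inferred.

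- The general sentence asks for events of a classification, and participants with such an event.
- The next sentence asks for event numbers and participant proportions regardless of MedDRA term, for five categories: any, serious, severe, related, and leading to discontinuation.
- The sentence after that asks for SOC and PT summaries of the same groups, with no measure stated.

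If the general sentence meant only the five totals, the sentence that follows would make its event count redundant. Read as a rule for all the summaries below it, each sentence has a purpose. That is the more natural reading, though not the only one.

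**2. Protocol against SAP.**

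| Summary | Protocol 9.0 (natural reading) | SAP 4.9.2 |
|---|---|---|
| Totals (any, serious, severe, related, drug discontinuation) | events and participants | events and participants |
| SOC and PT tables for the same groups | events and participants | participants only |

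The SAP's overall summary meets the first row and goes further (for example, dose reduced, interrupted, fatal). The second row is the gap. Section 7 does not mention it.

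**3. Size.** Inputs: planned N = 70 (Protocol 2.0, SAP 6), and weekly infusions from Week 0 to Week 24.

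- Infusions per participant: 24 + 1 = 25, which reproduces the figure in the Schedule of Activities.
- Maximum infusions: 70 × 25 = 1,750, if everyone completes treatment.

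Assume at most one event per term per infusion. A term reported by k participants is shown as k/70, while the number of events E can lie anywhere from k to 25k:

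| k | Shown in SOC/PT table | Range of E |
|---|---|---|
| 1 | 1 (1.4%) | 1 to 25 |
| 3 | 3 (4.3%) | 3 to 75 |
| 5 | 5 (7.1%) | 5 to 125 |
| 10 | 10 (14.3%) | 10 to 250 |

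For example, three participants with one reaction each give 3 × 1 = 3 events, and three with 20 each give 3 × 20 = 60. Both appear as 3/70 = 4.3%. These counts are illustrative; nothing in the documents predicts them.

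**4. What other planned output shows.**

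- *Overall summary.* If those reactions were judged related, the related-TEAE row would differ by 60 − 3 = 57 events at the same n. The excess is visible, but not its term.
- *Tables of terms reaching 5%.* 0.05 × 70 = 3.5, so at least 4 participants are needed. A term in 3 participants is absent, even at 75 events.
- *Time-to-onset tables.* There are three intervals. The SAP does not say whether a participant counts once per interval or once overall. At best a participant contributes 3 counts per term, against up to 25 events.
- *AE listing.* Each recorded event appears, unaggregated.

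**The case against.** The strongest reply is that the SAP complies. The only protocol sentence tying event counts to named categories is the one on totals, and the overall summary gives event numbers for all five. The SOC and PT sentences do not mention events. This reading is tenable, but it leaves the general sentence with no work to do.

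A reader might infer more than the documents support:

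- *That recurrence is hidden.* It is not. The overall summary would show the excess events, and with about 70 participants the listing allows attribution by term. SAP 4.9.1 also tabulates interruptions and withdrawals with reasons and event numbers.
- *That the once-only rule bars event counts.* It governs participant-level counting and is a normal rule for n (%). The gap comes from restricting event numbers to the overall summary.
- *That rash shows the problem.* Protocol 7.0 addresses further dosing after a related rash, so rash recurring over 25 infusions is a poor example. Infusion-site and other infusion-related events are better ones. The same section reports only one infusion-site reaction and no infusion reactions to date, so frequent recurrence should not be presumed.

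Two further points stand. The table shells are in a separate Data Presentation Plan, not available here, which might carry an event column, although the SAP wording suggests not. And an event count is only as good as the logging: Protocol 10.4.4 records onset and resolution dates but does not say whether a repeated reaction is a new AE or a continuing one.

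This is also an access programme with no formal hypothesis testing, with medical-monitor review and a DSMB. That limits the consequence but does not explain the undeclared difference.

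**Conclusion.** The point holds as a reporting gap worth correcting. On the more natural reading, Protocol 9.0 plans event counts by SOC and PT; SAP 4.9.2 gives them only as overall totals, and Section 7 is silent. What is missing is a tabulation of events by term. Aggregate event counts and event-level listings are still there.

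At N = 70, with all 25 infusions given and at most one event per term per infusion, one table entry can stand for up to a 25-fold range of events. The realised range will be smaller if participants stop early or if sites log repeats as one continuing AE. The conclusion does not rest on the illustrative 3 and 60; it follows from the choice of measure. No estimate, test or participant protection is affected.

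**What to change.** In SAP 4.9.2, add the number of events beside n (%) in the SOC and PT tables, at least for all, related and serious TEAEs, and carry this into the Data Presentation Plan shells. State how repeated reactions are counted, as separate AEs or one continuing AE, because the column means nothing without that rule. Keep n (%) as the lead figure and state in the time-to-onset tables whether a participant can count in more than one interval. If the sponsor prefers participant counts only, record and justify that in Section 7.

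The cost is one column from data already in the AE dataset, plus a sentence or two of text. The drawback is sensitivity to site logging practice. A rate per 100 infusions, using the infusion count from SAP 4.9.1, is an optional extra that neither document asks for.

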10.0 MONITORING AND QUALITY ASSURANCE

The investigator will monitor for possible known side effects as well as unexpected side effects of SLS-005. In addition to scheduled visits, the participant will be encouraged to keep in close communication with the SI and site staff via regular phone calls should they have any questions or experience any changes in their health between visits. Since SLS-005 is an experimental drug with possible unknown side effects, the participant should be encouraged to report all changes to the SI.

10.1 Ethical Conduct of the Program

This intermediate-size EAP will be conducted according to applicable Code of Federal Regulations including but not limited to provision of required IND safety reports and annual reports.

The intermediate-size EAP will also be conducted in accordance with GCP defined by the ICH and the ethical principles of the Declaration of Helsinki. The intermediate-size EAP will be conducted in

compliance with the protocol. The protocol and any amendments as well as the participant informed consent will receive central IRB approval prior to initiation. Personnel involved in conducting this protocol will be qualified to perform their respective task(s) as confirmed by the site and collection of required documentation.

10.2 Medical Monitor

The Medical Monitor will act as an expert point of reference for SLS-005 for both investigative sites and protocol team members. Safety concerns can be discussed with the Medical Monitor upon occurrence or awareness to determine if a participant should continue or discontinue SLS-005. The Medical Monitor will:

- Answer inclusion and exclusion questions from investigative sites
- Answer questions specific to the protocol
- Coordinate with the protocol team to ensure information is consistent
- Address safety issues across all sites and the protocol team

10.3 Adverse Events, Suspected Adverse Drug Reactions, and Serious Adverse Events

The Adverse Event (AE) definitions and reporting procedures provided in this protocol comply with all applicable United States Food and Drug Administration (FDA) regulations and ICH guidelines. The SI will carefully monitor each participant throughout the study for possible adverse events. All AEs will be documented on CRFs designed specifically for this purpose. It is also important to report all AEs, especially those that result in permanent discontinuation of the investigational product being studied, whether serious or non-serious.

10.3.1 Definitions of AEs and Suspected Adverse Drug Reactions

An AE is any unfavorable and unintended sign (including a clinically significant abnormal laboratory finding, for example), symptom, or disease temporally associated with a study, use of a drug product or device whether or not considered related to the drug produce or device. Adverse drug reactions (ADR) are all noxious and unintended responses to a medicinal product related to any dose. The phrase “responses to a medicinal product” means that a causal relationship between a medicinal product and an adverse event is at least a reasonable possibility, i.e., the relationship cannot be ruled out. Therefore, a subset of AEs can be classified as suspected ADRs, if there is a causal relationship to the medicinal product.

Examples of AEs include: new conditions, worsening of pre-existing conditions, clinically significant abnormal physical examination signs (e.g., skin rash, peripheral edema, etc.), or clinically significant abnormal test results (e.g., lab values or vital signs), with the exception of outcome measure results, which are not being recorded as adverse events in this trial (they are being collected, but analyzed separately). Stable chronic conditions (e.g., diabetes, arthritis) that are present prior to the start of the study and do not worsen during the trial are NOT considered adverse events. Chronic conditions that occur more frequently (for intermittent conditions) or with greater severity, would be considered as worsened and therefore would be recorded as adverse events.

Adverse events are generally detected in two ways:

1. Clinical: symptoms reported by the participant or signs detected on examination.

2. Ancillary Tests: abnormalities of vital signs, laboratory tests, and other diagnostic procedures (other than the outcome measures, the results of which are not being captured as AEs).

For purposes of this study, symptoms of progression/worsening of ALS, including 'normal' progression, will be recorded as adverse events.

The following measures of disease progression will not be recorded as adverse events even if they worsen (they are being recorded and analyzed separately): SVC results and ALSFRS-R results.

If discernible at the time of completing the AE log, a specific disease or syndrome rather than individual associated signs and symptoms should be identified by the SI and recorded on the AE log. However, if an observed or reported sign, symptom, or clinically significant laboratory anomaly is not considered by the SI to be a component of a specific disease or syndrome, then it should be recorded as a separate AE on the AE log. Clinically significant laboratory abnormalities, such as those that require intervention, are those that are identified as such by the SI.

Participants will be monitored for adverse events from the time they sign consent for the EAP until completion of their participation as defined in the SOA.

An unexpected adverse event is any adverse event, the specificity or severity of which is not consistent with the current Investigator's Brochure. An unexpected, suspected adverse drug reaction is any unexpected adverse event for which, in the opinion of the SI or Sponsor, there is a reasonable possibility that the investigational product caused the event.

10.3.2 Definitions of Serious Adverse Events (SAEs)

A SAE is defined as an adverse event that meets any of the following criteria:

1. Results in death.
2. Is life threatening: that is, poses an immediate risk of death as the event occurred.
 - a. This serious criterion applies if the study participant, in the view of the SI or Sponsor, is at immediate risk of death from the AE as it occurs. It does not apply if an AE that might hypothetically have caused death if it were more severe.
3. Requires inpatient hospitalization or prolongation of existing hospitalization.
 - a. Hospitalization for an elective procedure (including elective PEG tube/g-tube/feeding tube placement) or a routinely scheduled treatment is not an SAE by this criterion because an elective or scheduled "procedure" or a "treatment" is not an untoward medical occurrence.
4. Results in persistent or significant disability or incapacity.
 - a. This criterion applies if the "disability" caused by the reported AE results in a substantial disruption of the participant's ability to carry out normal life functions.
5. Results in congenital anomaly or birth defect in the offspring of the participant (whether the participant is male or female).
6. Necessitates medical or surgical intervention to preclude permanent impairment of a body function or permanent damage to a body structure.
7. Important medical events that may not result in death, are not life-threatening, or do not require hospitalization may also be considered SAEs when, based upon appropriate medical judgment, they may jeopardize the participant and may require medical or surgical

intervention to prevent one of the outcomes listed in this definition. Examples of such medical events include blood dyscrasias or convulsions that do not result in inpatient hospitalization, or the development of drug dependency or drug abuse.

An inpatient hospital admission in the absence of a precipitating, treatment-emergent, clinical adverse event may meet criteria for "seriousness" but is not an adverse experience, and will therefore, not be considered an SAE. An example of this would include a social admission (participant admitted for other reasons than medical, e.g., lives far from the hospital, has no place to sleep).

A serious, suspected adverse drug reaction is an SAE for which, in the opinion of the SI or Sponsor, there is a reasonable possibility that the investigational product caused the event.

The SI is responsible for classifying adverse events as serious or non-serious.

